8.4.4. Medically Attended Adverse Events

An MAAE is an AE that leads to an unscheduled visit to an HCP, including telephone calls. This would include visits to a study site for unscheduled assessments (eg, abnormal laboratory follow-up, COVID-19 [Section 8.1.8]) and visits to HCPs external to the study site (eg, urgent care, primary care physician). Investigators will review unsolicited AEs for the occurrence of any MAAEs. Unsolicited AEs will be captured on the AE page of the eCRF.

All cases of RT-PCR-confirmed ILI and/or confirmed COVID-19 will be recorded as MAAEs.

8.4.5. Influenza-like Illness

A protocol-defined ILI is determined by the occurrence of at least 1 respiratory illness symptom concurrently with at least 1 systemic symptom or the occurrence of any 2 or more respiratory symptoms.

Respiratory Symptoms		Systemic Symptoms	
1.	Sore throat	1. Body temperature > 37.2°C (> 99°F)	
2.	Cough/rhinorrhea/nasal congestion	2. Chills	
	$(\geq 1 \text{ of the } 3 \text{ symptoms count as})$	3. Tiredness	
	1 respiratory symptom)	4. Headache	
3.	Sputum production	5. Myalgia	
4.	Wheezing	6. Nausea/Vomiting	
5.	Difficulty breathing	7. Diarrhea	

A CDC-defined ILI is defined as body temperature \geq 37.8°C (100°F) accompanied by a cough and/or sore throat.

An RT-PCR-confirmed influenza infection is defined as a positive influenza result on a respiratory sample by RT-PCR done within 7 days of onset of protocol-defined ILI at any setting during the study period.

8.4.6. Suspicion of SARS-CoV-2 Infection

SARS-CoV-2 should be suspected if the participant experiences the acute onset or worsening of any one of the symptoms listed below (CDC 2021c):

- Fever (temperature ≥ 38.0 °C [100.4°F]) or chills (of any duration)
- Cough (of any duration)
- Shortness of breath and/or difficulty breathing (of any duration)
- Nausea, vomiting or diarrhea (of any duration)
- Fatigue (lasting \geq 48 hours)
- Muscle or body aches (lasting \geq 48 hours)
- Headache (lasting \geq 48 hours)
- New loss of taste and/or smell (lasting \geq 48 hours)
- Sore throat, congestion, or runny nose (lasting ≥ 48 hours)

Symptomatic COVID-19 is defined by the presence of one of the above CDC-listed symptoms (CDC 2021c) and a positive RT-PCR test on a respiratory sample. Asymptomatic SARS-CoV-2

infection is defined as a positive RT-PCR test on a respiratory sample in the absence of symptoms or a positive serologic test for anti-nucleocapsid antibody after a negative test result at the time of enrollment, with the serologic assay detecting previously resolved SARS-CoV-2 infections that may have occurred between visits, and the RT-PCR to detect active viral infection at the time of a visit. If participants are confirmed to have SARS-CoV-2 infection and are symptomatic or asymptomatic, the investigator will notify the participants' primary care physicians of the diagnosis and the local public health authorities as required per local regulations.

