1.3. Schedule of Events

 Table 1
 Schedule of Events

Visit Number	SCRN	1	2	3	4	5, 6, 7, 8	9	USV
Type of Visit	С	С	С	С	С	SC	С	С
Month Time Point	N/A				M1	M2-M5	M6	Up to M6
Visit Day	Screening ¹	D1 (Baseline) ¹	D4	D8	D29	D57, D91, D121, D151	D181/ EoS	N/A
Window Allowance (Days)	-28	N/A	-2	+3	-7 to +2	±5	±14	N/A
Informed consent form, demographics, concomitant medications, medical history	X							
Inclusion/exclusion criteria	X	X						
Blood collection for safety laboratory samples ²	X			X				
Full physical examination ³	X							
Axillary lymph nodes assessment (both arms) ⁴		X						
Symptom-directed physical examination ⁵		X		X	X		X	X
Vital sign measurements ⁶	X	X						
Electrocardiogram (ECG) ⁷		X						
Pregnancy testing ⁸	X	X						
Randomization		X						
Study vaccination (including 60-minute, post-dose observation period)		X ⁹						
Blood collection for humoral immunogenicity ¹⁰		X		X	X		X	
Blood collection for cellular immunogenicity ¹⁰		X		X	X		X	
Optional blood collection for genomics ¹¹		X						
Optional blood collection for transcriptomics ¹¹		X		X	X			
Blood sample for potential biomarker analysis ¹²			X					
Nasopharyngeal swab for virus detection ¹³		X						X
eDiary activation for recording solicited ARs (7 days) ¹⁴		X						

Visit Number	SCRN	1	2	3	4	5, 6, 7, 8	9	USV
Type of Visit	С	С	С	С	С	SC	С	С
Month Time Point	N/A				M1	M2-M5	M6	Up to M6
Visit Day	Screening ¹	D1 (Baseline) ¹	D4	D8	D29	D57, D91, D121, D151	D181/ EoS	N/A
Window Allowance (Days)	-28	N/A	-2	+3	-7 to +2	±5	±14	N/A
Review of solicited AR eDiary				X				
eDiary activation for Symptom Reporting eDiary ¹⁵		X						
Symptom Reporting eDiary for collection of symptoms of ILI and/or COVID-19 ¹⁶		Once weekly						
Follow-up safety call ¹⁷						X		
Recording of unsolicited AEs through Day 29		X		X	X			X
Recording of SAEs, AESIs, MAAEs, AEs leading to discontinuation, and concomitant medications relevant to or for their treatment ¹⁸		X		X	X	X	X	X
Recording of non-study vaccinations ¹⁸	X	X		X	X	X	X	X
Study completion							X	

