8.2. Immunogenicity Assessments

Blood samples for immunogenicity assessments will be collected at the time points indicated in the SoE (Table 1). Immunogenicity assessments will be performed for all participants. Immune response to influenza vaccine antigens will be using HAI assay, with potential utilization on microneutralization assay for influenza strains that do not perform favorably in the HAI assay. Immune responses to SARS-CoV-2 vaccine antigens will utilize either pseudovirus neutralization (PsVNA) nAb assay or multiplex bAb assay, depending on the timing of data delivery. The following analytes will be measured:

• Influenza: Serum antibody level as measured by HAI assay

- Influenza: Serum nAb level as measured by microneutralization assay as potential substitution to the HAI assay
- SARS-CoV-2: Serum nAb titers as measured by PsVNA and potentially serum binding antibody titers by ELISA or multiplex assay specific to the SARS-CoV-2 proteins
- Cellular immunogenicity in a subset of participants

Sample aliquots will be designed to ensure that backup samples are available and that vial volumes are likely to be adequate for future testing needs. The actual date and time of each sample will be collected. Unique sample identification will be utilized to maintain the blind at the laboratory at all times and to allow for automated sample tracking and housing. Handling and preparation of the samples for analysis, as well as shipping and storage requirements, will be provided in a separate study manual.

Measurement of antibody levels will be performed in a laboratory designated by the Sponsor.

According to the ICF (Section 11.1.6), excess serum from immunogenicity testing may be used for future research, which may be performed at the discretion of the Sponsor to further characterize the immune response to influenza and SARS-CoV-2 viruses, additional assay development, and the immune response across influenza viruses.

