9.4. Analysis Sets

The analysis sets are described in Table 8.

Table 8 Analysis Sets

Set	Description	
Randomization Set	The randomization set consists of all participants who are randomly assigned.	
FAS ¹	The FAS consists of all randomly assigned participants who receive the IP.	
PP Set ²	The PP set consists of all participants in the FAS who comply with the injection schedule, comply with the timings of immunogenicity blood sampling to have a baseline and at least 1 post-injection assessment, do not have influenza or SARS-CoV-2 infection at baseline and post-baseline up to Day 29 (as documented by positive RT-PCR testing result), and have no major protocol deviations and/or prohibited concomitant medication use (documented in the Section 6.5.3) that are prespecified with impacts on the immune response and should be excluded from the PP set.	
Safety Set ³	The safety set consists of all randomly assigned participants who receive the IP.	

Set	Description	
Solicited Safety Set ⁴	The solicited safety set consists of all participants in the safety set who contribute any solicited AR data.	

Abbreviations: AR = adverse reaction; FAS = full analysis set; IP = investigational product; PP = per-protocol.

- ¹ For the FAS, participants will be analyzed according to the group to which they were randomized.
- ² The PP set will be used as the primary analysis set for analyses of immunogenicity unless otherwise specified. Participants will be analyzed according to the group to which they were randomized.
- ³ The safety set will be used for all analyses of safety, except for the solicited ARs. Participants will be included in the vaccination group corresponding to what they actually received.
- ⁴ The solicited safety set will be used for the analyses of solicited ARs and participants will be included in the vaccination group corresponding to what they actually received.

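### Infection serology is defined but not planned, and the PP set removes only RT-PCR-positive cases up to Day 29, so infected participants stay in the SARS-CoV-2 analyses, chiefly at Day 181

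*Protocol*

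**What the plan says.** Section 8.4.6 gives asymptomatic SARS-CoV-2 infection two alternative limbs. The first is virological: "infection is defined as a positive RT-PCR test on a respiratory sample in the absence of symptoms". The second is serological: "a positive serologic test for anti-nucleocapsid antibody after a negative test result at the time of enrollment". The section also gives each limb its task. RT-PCR finds active infection at a visit, "with the serologic assay detecting previously resolved SARS-CoV-2 infections that may have occurred between visits".

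The rest of the protocol bears on this as follows.

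- **Analytes (Section 8.2).** The SARS-CoV-2 entry reads "SARS-CoV-2: Serum nAb titers as measured by PsVNA and potentially serum binding antibody titers by ELISA or multiplex assay specific to the SARS-CoV-2 proteins". Nucleocapsid is not named, and the binding-antibody assay is only a possibility. The safety laboratory list in Section 8.1.5 has no infection serology.
- **Schedule of Events (Section 1.3).** The row "Blood collection for humoral immunogenicity" is marked at Days 1, 8, 29 and 181. The row "Nasopharyngeal swab for virus detection" is marked at Day 1 and at unscheduled visits only. The swab footnote ties later swabs to symptoms or a suggestive medically attended event; Section 4.1 adds testing at any unscheduled visit.
- **PP set (Section 9.4).** Infection up to Day 29 removes a participant, but only "as documented by positive RT-PCR testing result".
- **Use.** Section 9.5.3 bases immunogenicity on the PP set. Section 3 makes SARS-CoV-2 titers, fold rises and seroresponse secondary endpoints at Day 29 and at all evaluable time points, and Section 9.6.2 carries them through Day 181.

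**The concern.** The protocol itself treats RT-PCR as insufficient between visits and relies on serology to fill the gap. It then plans no test that could supply either the negative enrollment result or the later positive one. The PP rule has no place for a serologic finding either, so an infection that met the second limb would leave the participant in the set.

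The PP rule also stops at Day 29, while the analyses run to Day 181. A later infection stays in even when RT-PCR has confirmed it.

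The SARS-CoV-2 endpoints are antibody titers, which infection also raises. A retained infection is read as vaccine response and can lift the geometric mean titer (GMT), the fold rise over Day 1 (GMFR) and the seroresponse rate. Only Group 2 (mRNA-1010 plus placebo) receives no SARS-CoV-2 antigen. A rise there has no vaccine cause, and it narrows the contrast with the other arms.

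**Working it through.** **Step 1: which infections are removed from the PP set, following the text as written**

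| Infection | Detected by a planned test? | Removed from PP set? |
|---|---|---|
| Present at Day 1 swab | Yes, universal RT-PCR | Yes |
| After Day 1 up to Day 29, RT-PCR positive (symptoms, medical attendance, unscheduled visit, incidental) | Yes | Yes |
| After Day 1 up to Day 29, never swabbed | No | No |
| After Day 29, RT-PCR positive | Yes | No, the rule ends at Day 29 |
| After Day 29, never swabbed | No | No |

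**Step 2: inputs.** The protocol gives no infection rate, detection share or fold rise, and no figure of its own to reproduce on this point. All of the following are assumptions:

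- infected by Day 29: 1-3%; by Day 181: 10-30%
- share of infections never swabbed: 30-50%
- titer multiple caused by an infection, g: 4 to 10

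**Step 3: effect on one arm.** If a share f of an arm carries an unrecognised infection that multiplies titer by g, the mean log titer rises by f × log g, so the GMT is multiplied by g^f. The GMFR is multiplied by the same factor, because Day 1 titers are unaffected.

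| Visit | Infected × never swabbed = f | g | g^f |
|---|---|---|---|
| Day 29, low | 1% × 30% = 0.3% | 4 | 1.004 |
| Day 29, high | 3% × 50% = 1.5% | 10 | 1.035 |
| Day 181, low | 10% × 30% = 3% | 4 | 1.04 |
| Day 181, middle | 20% × 30% = 6% | 4 | 1.09 |
| Day 181, middle | 20% × 50% = 10% | 10 | 1.26 |
| Day 181, high | 30% × 50% = 15% | 10 | 1.41 |

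Unswabbed infections alone thus inflate a single-arm GMT by about 0.4-3.5% at Day 29 and 4-41% at Day 181. A seroresponse percentage can rise by at most f: up to 1.5 points at Day 29 and 15 points at Day 181.

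**Step 4: confirmed infections after Day 29.** Take 20% infected by Day 181 and 2% by Day 29, so 18% arise after Day 29. If 50-70% of these are swabbed and positive, 9.0-12.6% of the arm is RT-PCR-confirmed and still in the PP set. Unswabbed infections at the same setting are 6-10%. Confirmed late cases are therefore about as numerous as silent ones, or more so. Together they make 12.6% + 6% = 18.6% or 9% + 10% = 19%, giving 4^0.186 = 1.29 to 10^0.19 = 1.55. Some treated cases may leave the PP set because Section 6.5.3 lists antivirals, which would lower this.

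**Step 5: contrasts between arms.** With a common f, the ratio of two arms shifts by (g₁/g₂)^f.

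- Equal g, as a first approximation for arms that all receive a SARS-CoV-2 antigen: factor 1, so the effect cancels.
- Group 2 at g = 10 against a boosted arm at g = 4: 2.5^0.10 = 1.10 when f = 10%, and 2.5^0.015 = 1.014 when f = 1.5%.

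**The case against.** The strongest reply is that the protocol leaves room for the test. The Schedule of Events lists collections, not assays, so the lack of a nucleocapsid row proves little. Serum is drawn at every relevant visit, backup aliquots are kept, and a "multiplex assay specific to the SARS-CoV-2 proteins" could include nucleocapsid. Sample analysis is referred to a Laboratory Manual that is not at hand. All of this stands. A reader might infer that the serologic limb can never be met; the documents do not support that. They support only that no section plans the test.

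Second, surveillance is not weak. Symptoms are prompted weekly through Day 181, any one listed symptom raises suspicion, and medically attended events and unscheduled visits also lead to swabs. This limits the silent share. It does nothing for confirmed cases after Day 29, which the PP rule keeps.

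Third, randomization balances infections on average, and the contrasts of most interest (mRNA-1073 against mRNA-1273 alone or co-administered) are between boosted arms. This stands too, and Step 5 agrees with it. Day 29, which serves the lead immunogenicity objective and the interim analysis, is little affected, and Section 9.2 tests no hypotheses.

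Fourth, a reader might infer that the exploratory infection count is incomplete. Its endpoint in Section 3 is laboratory-confirmed clinical influenza and COVID-19, so missed asymptomatic infections do not make it so.

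Finally, sensitivity analyses often belong in the SAP. However, which tests are run and on which samples is protocol content, and the mismatch between Sections 8.4.6 and 9.4 is in the protocol itself.

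**Conclusion.** The point holds as a mismatch within the protocol. Section 8.4.6 relies on anti-nucleocapsid seroconversion that no section plans, and Section 9.4 recognises only RT-PCR and only up to Day 29. Post-baseline infections never swabbed, and RT-PCR-confirmed infections after Day 29, remain in the SARS-CoV-2 GMT, GMFR and seroresponse analyses.

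The consequence is small at Day 29 and possibly material for absolute levels at Day 181. The Day 181 range of 4-41% counts unswabbed infections only. Every rate behind these figures is assumed, so they show an order of magnitude and are not forecasts. Comparisons among the five arms given a SARS-CoV-2 antigen are largely protected; comparisons with Group 2 are less so. The documents do not support reading this as a threat to the Day 29 data used for dose selection.

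**What to change.** 1. In Section 8.2, name anti-nucleocapsid testing on the Day 1, Day 29 and Day 181 serum already drawn, or state that the multiplex panel includes nucleocapsid and will be run at those visits.
2. Align Section 9.4 with Section 8.4.6. For the SARS-CoV-2 endpoints, add a sensitivity analysis that drops a participant's results from the visit at which infection is shown by RT-PCR or by nucleocapsid seroconversion, through Day 181.
3. Summarise baseline nucleocapsid status by arm. Exclusion criterion 14 bars only known infection within 90 days, so some participants may be positive at Day 1. They cannot seroconvert, and only RT-PCR can identify a new infection in them.
4. If the test will not be run, delete the serologic limb and state that asymptomatic infection is not systematically ascertained. The Day 29 limit of the PP rule still needs the RT-PCR part of item 2.

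The cost is one assay on existing serum, with no new visit or blood draw, and a slightly smaller Day 181 set in the sensitivity analysis. The alternative in item 4 needs no assay.

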8.4.7. Adverse Event of Special Interest

An AESI is an AE (serious or nonserious) of scientific and medical concern specific to the Sponsor's product or program for which ongoing monitoring and immediate notification by the investigator to the Sponsor is required and documentation is in the form of a case narrative. Such events may require further investigation to characterize and understand them.

Section 11.3 (Appendix 3) provides a list of AESIs pertinent to this study.

All AESIs will be collected through the entire study period and must be reported to the Sponsor or designee immediately and in all circumstances within 24 hours of becoming aware of the event via the electronic data capture (EDC) system. If a site receives a report of a new AESI from a study participant or receives updated data on a previously reported AESI at a time after the eCRF has been taken offline, then the site can report this information on a paper AESI form using the SAE Mailbox, or the SAE Fax line (Section 8.4.13).

8.4.7.1. Anaphylaxis

All suspected cases of anaphylaxis should be recorded as MAAEs and reported as an SAE, based on the criteria for a medically important event, unless the event meets other serious criteria. As an SAE, the event should be reported to the Sponsor or designee immediately and in all circumstances within 24 hours per Section 8.4.13. The investigator will submit any updated anaphylaxis case data to the Sponsor within 24 hours of it being available. For reporting purposes, a participant who displays signs or symptoms consistent with anaphylaxis (as described below) should be reported as a potential case of anaphylaxis. This is provided as general guidance for investigators and is based on the Brighton Collaboration case definition (Rüggeberg et al 2007).

Anaphylaxis is an acute hypersensitivity reaction with multi-organ system involvement that can present as, or rapidly progress to, a severe life-threatening reaction. It may occur following exposure to allergens from a variety of sources.

Anaphylaxis is a clinical syndrome characterized by the following:

- Sudden onset AND
- Rapid progression of signs and symptoms AND
- Involves 2 or more organ systems, as follows:
 - Skin/mucosal: urticaria (hives), generalized erythema, angioedema, generalized pruritus with skin rash, generalized prickle sensation, and red and itchy eyes.
 - Cardiovascular: measured hypotension, clinical diagnosis of uncompensated shock, loss of consciousness or decreased level of consciousness, and evidence of reduced peripheral circulation.
 - Respiratory: bilateral wheeze (bronchospasm), difficulty breathing, stridor, upper airway swelling (lip, tongue, throat, uvula, or larynx), respiratory distress, persistent dry cough, hoarse voice, sensation of throat closure, sneezing, and rhinorrhea.
 - **Gastrointestinal:** diarrhea, abdominal pain, nausea, and vomiting.

8.4.7.2. Myocarditis/Pericarditis

A case of suspected, probable, or confirmed myocarditis, pericarditis, or myopericarditis should be reported as an AESI, even if it does not meet criteria per the CDC case definition. The event should also be reported as an SAE if it meets seriousness criteria (Section 8.4.2). The CDC case definition is provided in Section 11.4 (Appendix 4) as guidance.

8.4.8. Recording and Follow-up of Pregnancy

Female participants who have a positive pregnancy test at Screening should not be enrolled; participants who have a positive pregnancy test at any time during the study should receive no further dosing with IP but should remain in the study and be monitored for safety.

Details of all pregnancies in female participants will be collected after the start of study treatment and until the end of their participation in the study. If a pregnancy is reported, the investigator should inform the Sponsor within 24 hours of learning of the pregnancy and should follow the procedures outlined in this section. Abnormal pregnancy outcomes (eg, spontaneous abortion, fetal death, stillbirth, congenital anomalies, ectopic pregnancy) will be considered as SAEs.

Pregnancies occurring in participants after enrollment must be reported to Sponsor or designee within 24 hours of the site learning of its occurrence, using the paper Pregnancy Reporting Form provided by the Sponsor. If the participant agrees to submit this information, the pregnancy must be followed to determine the outcome, including spontaneous or voluntary termination, details of the birth, and the presence or absence of any birth defects, congenital abnormalities, or maternal

and/or newborn complications. This follow-up should occur even if intended duration of the safety follow-up for the study has ended. Pregnancy report forms will be distributed to the study site to be used for this purpose. The investigator must immediately (within 24 hours of awareness) report to the Sponsor any pregnancy resulting in an abnormal outcome according to the procedures described for SAEs.

8.4.9. Eliciting and Documenting Adverse Events

The investigator is responsible for ensuring that all AEs and SAEs are recorded in the eCRF and reported to the Sponsor.

Solicited ARs will be collected from Day 1 through 7 days after vaccination. Other (unsolicited) AEs will be collected from Day 1 through 28 days after vaccination.

The MAAEs, AESIs, AE leading to withdrawal, and SAEs will be collected from participants as specified in the SoE (Table 1) until the end of their participation in the study. Any AEs occurring before receipt of IP will be analyzed separately from AEs occurring after receipt of the study vaccine(s).

At every study site visit or telephone contact, participants will be asked a standard question to elicit any medically related changes in their well-being (including respiratory viral infection and COVID-19 symptoms) according to the scripts provided. Participants will also be asked if they have been hospitalized, had any accidents, used any new medications, changed concomitant medication regimens (both prescription and over-the-counter medications), or had any non-study vaccinations.

In addition to participant observations, physical examination findings, or data relevant to participant safety classified as an AE will be documented on the AE page of the eCRF.

After the initial AE/SAE report, the investigator is required to proactively follow each participant at subsequent visits/contacts. All AEs and SAEs will be treated as medically appropriate and followed until resolution, stabilization, the event is otherwise explained, or the participant is LTFU (as defined in Section 7.4). All contacts, or contact attempts, concerning follow-up of AEs/SAEs should be recorded in the participant's source documentation.

